#### 4.2 Inclusion and exclusion criteria

##### Key Inclusion Criteria:

1. Men and women age 18 years and older and able to speak and read English
2. Must be in good health and not knowingly have a cancer at the time of study inclusion

##### Key Exclusion Criteria:

1. Head and Neck cancer diagnosis at the time of the oral cancer screening
2. Low DNA quantity found in mouthwash/saliva sample
3. Incomplete questionnaire data
4. Cancer diagnosis within the last 2 years

### 5.0 Risks to Participants

Risk to the subject is breach of confidentiality. In order to minimize this risk, all information obtained from or for this research study will be kept as confidential as possible. Identification of questionnaire data and saliva specimens will be assigned a coded study number and files will be kept secure.

### 6.0 Potential Benefits to Participants

No direct benefit will be gained by subjects, except for the satisfaction they might experience by participating in a medical research study. Benefits to society will be those associated with a better understanding of the effects of ancestry on motivation to quit smoking and screen for lung cancer.

**7.0 Provisions to Maintain the Confidentiality of Data**

All specimens and associated data (questionnaire, cancer screening results, urine specimen, as well as mouthwash samples) will be stored with a unique ID only and not with subject identifiers. Identifiable information will never be placed on specimens or associated data (laboratory or questionnaire data).

**8.0 Costs to Participants**

Not Applicable

**9.0 Consent Process**

On-Site Recruitment: Local Information tables will be set up in various locations such as senior centers, community recreation centers, churches, community health fairs and neighborhood block meetings. The information table will be manned by research staff who will explain the research studies conducted in the [name] Lab and the purpose of the participant recruitment.

Recruitment initiated by Phone-Call: Research staff will call participants that enrolled in 14-814 and indicated their interest in future research opportunities and briefly describe the study objectives and rationale. The research staff will answer all questions asked by the potential participant and an invitation will be extended to participate in this study. If he/she agrees to enroll in this study, they will sign an informed consent document, questionnaires will be administered, and biological samples will be collected by trained research staff.

As part of the informed consent process, all participants recruited in this study that have not been enrolled in 14-814 will be given an opportunity to join the 14-814 registry study. On-Site Recruitment as described in section 9.0 of that protocol will be followed.

**10.0 Off-Study Criteria**

Participants will only be removed from the study if a cancer diagnosis is made at the time of the oral cancer screening or if the participant is re-contacted for other research opportunities within the [name] Lab and they had a cancer diagnosis subsequent to joining the study.

**11.0 Drugs and Devices**

Not Applicable

**12.0 Multi-Site Research Study**

This study will be conducted at sites across the northeastern region of the country. Survey data and biological specimens collected from NYC and Philadelphia, will be housed at FCCC. In an effort to minimize a breach in participant confidentiality, all site-PIs and their respective team members will: provide current Human Subjects Training and be given access to both Presage Lite and REDCap, where they will securely enter patient information and complete study related questionnaires. Paper copies are also available for back up if needed. Scanned copies of signed consent forms will be emailed to the study coordinator at FCCC using HIPAA compliant networks and stored in a password protected file on FCCC stored on a HIPAA compliant institutional network drive. Only coded bio-specimens will be sent to FCCC where all laboratory procedures will take place.

Adverse events that take place at an external site will first be reported to the respective site's IRB followed by FCCC's IRB. All study findings will be reported under the blanket of the African Caribbean Cancer Consortium, a collaborative research group where [name] is the PI.

### 13.0 Statistical Analysis

**Aim 1:** Variance stabilizing and normalizing transformations will be applied when appropriate. Descriptive statistics for demographic variables will be presented. The range and mean concentrations of free (NNAL), conjugated (NNAL-Gluc) and total (NNAL+NNAL-Gluc) biomarkers will be summarized by genotype. These concentrations as well as the ratio of NNAL-Gluc:NNAL concentrations will be correlated with each AIM after adjusting for smoking dose (pack-years), age and recruitment setting (clinic vs. community) using analysis of variance. A similar analysis will be done by correlating these variables with each haplotype block. In addition, multiple linear regression will be used to correlate NNAL concentration with proportion of African ancestry after adjusting for smoking dose, age and recruitment setting. To account for multiple testing, the Benjamini-Hochberg (BH) method will be used to control the false discovery rate (FDR). All tests will be two-sided and tests with  $FDR \leq 10\%$  will be considered to be statistically significant.

**Sample Size and Power:** With 360 samples split in a 1:3 ratio between the minor and major allele groups, we will have 80% power to detect an effect size of 0.45 in mean NNAL concentration (total) between the groups using a two-sided test at a significance level of 0.005. This computation is based on a standard deviation of 1 for NNAL concentrations (on the log2-scale) from pilot studies. An effect size of 0.45 corresponds to a 1.37-fold change in NNAL concentration between groups. Similarly, with 360 samples split in a 1:3 ratio between the minor and major allele groups, we will have 80% power to detect an effect size of 1.09 in mean NNAL concentration ratio between the groups using a two-sided test at a significance level of 0.005. This computation is based on a standard deviation of 2.44 for NNAL concentration ratios (on the log2-scale) from pilot studies. An effect size of 1.09 corresponds to a 2.13-fold change in NNAL expression between groups. A significance level of 0.005 results in 1 false discovery per 200 non-differentially expressed SNPs.

**Aim 2:** For each SNP, nicotine dependence (as determined by high-very high FTND scores: 6-10) will be modeled using genotype after adjusting for smoking dose (pack-years), age and recruitment setting using logistic regression (LR). Sensitivity, specificity and prediction accuracy (along with 95% confidence bounds) will be used to characterize the precision of binary predictions from LR. Multiple linear regression will be used to correlate the proportion of African ancestry with FTND score (low vs. high) after adjusting for smoking dose, age and recruitment setting. All tests will be two-sided and the Benjamini-Hochberg method will be used to account for multiple testing. Secondary outcomes will include cigarettes per day, age at initiation, and intention to quit. To account for the potentially large number of SNPs resulting from this univariate analysis, penalized logistic regression (PLR) will be used to develop a prediction model for nicotine dependence using these SNPs. PLR has been demonstrated to have excellent power to identify covariate effects as well as superior prediction accuracy compared to competing methods like Classification and Regression Trees and Multifactor Dimensionality Reduction. Sensitivity, specificity and prediction accuracy (along with 95% confidence bounds) will be used to characterize the precision of binary predictions from PLR. AUC curves (along with 95% confidence bounds) will be used to characterize the predictive value of models from these methods. A participant whose predictive probability is  $> 0.5$  will be classified as having high nicotine dependence; however, alternative thresholds will also be evaluated in this

analysis. In addition, the performance of each model will be evaluated using leave-one-out cross validation. All computations will be performed using R statistical language and environment.

**Sample Size and Power:** With 180 subjects each in the low-medium (scores 0-5) and high-very high (scores 6-10) nicotine dependence groups, we will have 80% power to detect a difference in the range of 0.14-0.19 (in minor allele frequency between groups in SNPs of interest) at the 0.005 significance level. This calculation assumes a 10-40% minor allele frequency in the low nicotine dependence group.

**Aim 3:** Variance stabilizing and normalizing transformations will be applied to the data as appropriate. Analysis of variance will be used to identify the individual and interaction effects of factors on each outcome measure. The Benjamini-Hochberg FDR method will be used to adjust for multiple tests involving each factor or interaction across the various outcome measures, and each test with an FDR  $\leq 10\%$  will be considered significant. The primary study analyses will be a 2 (Risk) x 2 (Ancestry) factorial ANOVA. With this statistical approach, we will be able to test for main effects of Risk and Ancestry, as well as Risk x Ancestry interactions. The primary outcome measure will be motivation to quit; perceived risk, cancer worry, and psychological distress will serve as secondary outcomes. In addition to this primary analysis, we will also consider including covariates (e.g., demographics, numeracy, FTND, study site, gender, age) to control for external sources of variation. Finally, we will be able to explore possible moderating effects of these covariates. Although of course, the proposed study is not powered to detect such effects, such exploratory findings may be important when deciding next steps in formally utilizing the results to develop interventions aimed at increasing knowledge of genetic lung cancer risk.

**Sample size and power:** Power computations for this aim are based on the 2 x 2 factorial design described above. With 90 participants per experimental condition (combination of genetic risk and ancestry), we would be able to detect an effect size of 0.685 due to genetic risk or ancestry at a significance level of 0.0125 with 80% power. Similarly, we would be able to detect an effect size of 0.895 due to an interaction between genetic risk and ancestry at a significance level of 0.0125 with 80% power. A significance level of 0.0125 has been used to account for the four outcome measures of interest in this aim and the calculations are based on a standard deviation of 1.37 for motivation to quit smoking from the literature.

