## 2.0 Objectives

Aim 1: Identify ancestry-informative variants in tobacco metabolism and detoxification pathway genes that correlate with metabolic/detoxification capacity in AA smokers.

Aim 2: Identify ancestry-informative variants in tobacco addiction pathway genes that correlate with measures of nicotine dependence in AA smokers.

Aim 3: Explore the possibility that genetic feedback about increased lung cancer risk associated with African American ancestry may influence perceived risk, cancer worry, acute psychological distress, and motivation to quit.

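### The marker association models in Aims 1 and 2 leave out proportion of African ancestry, so a marker with no effect of its own can be flagged through overall ancestry

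*Combined protocol and SAP*

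**What the plan says.** Section 2.0 sets Aim 1 as "Identify ancestry-informative variants in tobacco metabolism and detoxification pathway genes that correlate with metabolic/detoxification capacity in AA smokers" and Aim 2 as "Identify ancestry-informative variants in tobacco addiction pathway genes that correlate with measures of nicotine dependence in AA smokers". Both aims therefore concern variants selected for being ancestry-informative and located in named pathways.

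Section 13.0 gives the marker models:

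- Aim 1, single markers: the NNAL concentrations and the NNAL-Gluc:NNAL ratio "will be correlated with each AIM after adjusting for smoking dose (pack-years), age and recruitment setting (clinic vs. community) using analysis of variance".
- Aim 1, haplotypes: "A similar analysis will be done by correlating these variables with each haplotype block". No further covariate is named.
- Aim 2, single SNPs: nicotine dependence "will be modeled using genotype after adjusting for smoking dose (pack-years), age and recruitment setting using logistic regression (LR").

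Ancestry proportion is an analysis variable in both aims, but only in separate regressions without a marker. In Aim 1, "multiple linear regression will be used to correlate NNAL concentration with proportion of African ancestry"; in Aim 2, "Multiple linear regression will be used to correlate the proportion of African ancestry with FTND score (low vs. high").

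Both aims use Benjamini-Hochberg, and Aim 1 states a 10% threshold. Aim 1's power paragraph adds: "A significance level of 0.005 results in 1 false discovery per 200 non-differentially expressed SNPs". The documents mention no principal components, genomic control or other protection against confounding by ancestry.

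**The concern.** Section 3.0 defines ancestry-informative markers as polymorphisms whose frequencies differ between African Americans and Whites. In an admixed sample, people with more African ancestry carry more of the African-frequent allele at every such marker, so all the markers are correlated with one background variable. If that variable is related to the outcome by any route other than the tested marker, including through other markers that are truly active, the tested marker inherits an association.

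The documents give some reason to expect such a link. Section 3.0 reports that the NNAL-Gluc:NNAL ratio is higher in Whites than in African Americans. That is a between-race difference, not a gradient shown within African American smokers. For total NNAL and nicotine dependence, Section 1.0 raises a genetic contribution only as a possibility.

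What is at stake is attribution. The aims are about variants in pathway genes, and Section 3.0 presents such variants as able to alter gene expression and function. Without ancestry in the model, a hit cannot be credited to the pathway gene rather than to overall ancestry. Benjamini-Hochberg does not help, because it takes the p-values of null markers as valid. The separate ancestry regressions do not help either, because they contain no marker.

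**Working it through.** **1. The plan's own figures reproduce.** With 90 vs 270 participants and two-sided alpha 0.005, the noncentral t gives power 0.808 for 0.45 (SD 1) and 0.800 for 1.09 (SD 2.44). The Aim 2 detectable difference at 180 per group is 0.145 at minor-allele frequency (MAF) 0.10 and 0.191 at 0.40, against the stated 0.14-0.19. Also 200 × 0.005 = 1. The problem is in the analysis model, not in this arithmetic.

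**2. Inputs that must be assumed.** The documents give no ancestry distribution, panel size, frequency differences or within-sample gradient. Assumed here:

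- Ancestry mean 0.8 and SD s = 0.12.
- Difference d between ancestral allele frequencies either varying over 0.1-0.5 or fixed at 0.5.
- 200 markers (the denominator in Aim 1's power paragraph, not a stated panel size), with 5 or 10 active at 0.45 SD.
- Outcome gradient between 0% and 100% ancestry of 0, 0.5, 1 or 2 SD. The last is an upper limit: 2² = 4-fold for total NNAL and 2^(2 × 2.44) ≈ 29-fold for the ratio.

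A false finding here means a marker with no effect of its own.

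**3. One null marker in Aim 1, alpha 0.005.** With MAF p, the squared marker-ancestry correlation is r² = 4d²s² / [2p(1−p) + 2d²s²]. The outcome variance due to ancestry is R² = (gradient × s)². The noncentrality is N·r²R²/(1 − r²R²), referred to chi-square on 1 df.

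Example with d = 0.5, p = 0.30 and gradient 1 SD: r² = 0.0144/0.4272 = 0.0337; R² = 0.0144; noncentrality = 360 × 0.000485 ≈ 0.175; rejection rate 0.009.

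Over the feasible MAF range 0.10-0.50 with d = 0.5, the rate is 0.006-0.007 at 0.5 SD, 0.008-0.015 at 1 SD and 0.021-0.062 at 2 SD. Outer cases run from 0.005 to 0.32 (the latter at d = 0.7, s = 0.15, p = 0.14, 2 SD).

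**4. Realised false discovery rate in Aim 1, Benjamini-Hochberg at 10%.** Simulation of 1,200 trials per case, N = 360, Monte Carlo SE 0.003-0.010. Ranges span 5 and 10 active markers.

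| Gradient (SD) | d varying 0.1-0.5 | all d = 0.5 | true ancestry in model, either setting |
|---|---|---|---|
| 0 | 0.10 | 0.14-0.15 | 0.09-0.10 |
| 0.5 | 0.12 | 0.16-0.17 | 0.10 |
| 1 | 0.13-0.14 | 0.21-0.22 | 0.09-0.10 |
| 2 | 0.22-0.25 | 0.38-0.43 | 0.10 |

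In the d = 0.5 column the rate exceeds 10% even at zero gradient, because active markers leak into inactive ones through shared ancestry. Outer cases, from 0 to 2 SD, are 0.10-0.16 (d = 0.3, s = 0.10) and 0.34-0.76 (d = 0.7, s = 0.15).

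**5. Aim 2, one null SNP, alpha 0.005.** Simulation of 20,000 logistic fits per case, 180 vs 180, d = 0.5. Odds ratios between 0% and 100% ancestry were 2.5, 6.1 and 38 (about 1.1, 1.2 and 1.4 per 10 percentage points). Rejection rates are 0.006 / 0.008 / 0.019 at MAF 0.30 and 0.005 / 0.011 / 0.037 at MAF 0.10. Outer cases run from 0.005 to 0.18. With ancestry added the rate is 0.004-0.006.

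**6. Power with ancestry added.** The variance inflation is 1/(1 − r²), so the effect is scaled by √(1 − r²).

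| Marker-ancestry r | Inflation | Power, 0.45 | Power, 1.09 (ratio) | Detectable effect (SD) |
|---|---|---|---|---|
| 0 | none | 81% | 80% | 0.447 |
| 0.2 | 4% | 79% | 78% | 0.456 |
| 0.3 | 10% | 76% | 75% | 0.468 |
| 0.41-0.43 | 20-23% | 70-71% | 69-70% | 0.490-0.495 |

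At s = 0.12 and d = 0.5, r is at most 0.28 (at MAF 0.10). The last row arises only in the outer cases.

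**The case against.** The strongest reply is that no stated error rate is broken for what the plan literally sets out to test. Both aims speak of variants that correlate with the phenotype, and the false-discovery sentence refers to SNPs with no difference between groups. A SNP that differs because of ancestry is not in that set. The inflation appears only when a false finding is defined as a marker with no effect of its own. This stands as far as it goes: for plain correlation the 0.005 level is correct. It does not meet the purpose of the aims, which is to point to pathway genes that Section 3.0 treats as functional.

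Second, the outcome side is undocumented within African American smokers, and with varied frequency differences the effect is small unless the gradient is steep. With 5 active markers, the mean number of false hits among 200 rises only from 0.52 to 0.59 to 0.67 at gradients of 0, 0.5 and 1 SD. The larger false discovery rates need 2 SD or uniformly large frequency differences. This also stands, and it is why no single figure is claimed.

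Third, the support for Aim 2 is thinner. Its decision rule is Benjamini-Hochberg, but only single-test rates were computed. The haplotype covariates are inferred from the reference to a similar analysis. Aim 3's randomised comparison is not affected.

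Fourth, the 0.09-0.10 after adjustment assumes true ancestry is known. A poor estimate corrects less, as set out under the fix.

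**Conclusion.** The concern holds. The omission is certain for the per-AIM and per-SNP models and is the natural reading for haplotype blocks. Nothing else in the documents guards against it. The direction follows from how the markers are chosen, provided ancestry is linked to the outcome by some route other than the tested marker. With no direct gradient and modest frequency differences, the inflation is essentially nil.

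The size is unknown. Under the main assumptions, Aim 1's false discovery rate for locus-specific effects lies between its nominal 10% and about 25% with varied differences, and between about 14% and 43% with all differences at 0.5. Neither Aim 1's 10% nor the one-in-200 statement is assured for that target. This should be fixed. It does not invalidate the stated sample size arithmetic.

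**What to change.** Add estimated proportion of African ancestry as a covariate in every per-AIM, haplotype and per-SNP association model in Aims 1 and 2, where possible estimated from markers other than the one tested. State which markers estimate it; the documents do not say. Restate power with the term included, using the losses tabulated above.

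The cost is mainly SAP wording, since ancestry proportion is already an analysis variable. The quality of the estimate matters:

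- Estimated from the other 199 panel markers (reliability about 0.77 with differences 0.1-0.5, 0.88 with all at 0.5), the false discovery rate is 0.09-0.11.
- With a 50-marker panel (reliability 0.45), it is 0.12 at 2 SD, against 0.19 unadjusted.
- With an independent estimate of reliability 0.85, it is 0.09-0.11 in the two main settings and 0.105-0.147 in the d = 0.7, s = 0.15 case.
- Leaving the tested marker in the estimate cost at most about 2 points of power.

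The panel-based figures assume known ancestral frequencies and markers that are independent given ancestry. A small panel clustered in a few genes would do worse, might absorb part of a marker's own effect, and could require additional markers.

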#### *4.1 Subject Recruitment and Data Collection*

**Face-to-face:** As previously described in IRB 11-880, study subjects will be recruited from various locations throughout the metropolitan area of the aforementioned study cities (for example, stores, shops, community centers, senior centers, health fairs etc.). Based on results from protocol 11-880, we have determined that "on-site" (face-to-face) recruitment from various locations throughout the Philadelphia metropolitan area works best for control recruitment; subsequently, we will use this method as the primary recruitment method for this study. Primary care and specialty clinics within TUHS (e.g. ENT and Pulmonary clinics) to identify current smokers. We will also utilize study flyers (attached in recruitment section) throughout the TUHS with the contact information for study staff. If the individual calls in we will answer any questions and schedule their enrollment during their next appointment at a TUHS clinic.

After informed consent is obtained Mouthwash/Saliva samples will be collected at the completion of the study questionnaire. Participants will be supplied with a 50 mL falcon tube containing 10ml of scope. Participants will be instructed to gargle while tilting to the back of the throat for 30-60 seconds before spitting it back into a separate tube. Participants will be required to have refrained from eating and drinking at least 30 minutes prior to performing the mouthwash rinses. All mouthwash samples will be transported at 4 degrees Celsius (on ice packs) to the laboratory where they will be processed. All samples will be labeled with a unique ID number corresponding to the questionnaire but without personal identifiers. For urine collection, study staff will instruct the participant on how to conduct a clean catch urine sample and the participant will self-collect in nearest rest room.

All participants with a history of cancer screening (e.g. Pap test, breast mammography [females], PSA and/or DRE [males], oral or skin cancer screening, etc.) within the past 12 months will be asked to sign an authorization to request information from another facility. We will use the standard authorization form used by Fox Chase

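### The Aim 1 and Aim 2 association models adjust for clinic versus community but not for city, so null markers could be associated with NNAL or FTND if both marker and outcome differ between Philadelphia and NYC

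*Combined protocol and SAP*

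**What the plan says.** All references are to the combined protocol and SAP.

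- **Aim 1, Section 13.0.** Each ancestry-informative marker is related to the NNAL measures "after adjusting for smoking dose (pack-years), age and recruitment setting (clinic vs. community) using analysis of variance". Haplotype blocks get a similar analysis. A separate regression will "correlate NNAL concentration with proportion of African ancestry after adjusting for smoking dose, age and recruitment setting".
- **Aim 2, Section 13.0.** High nicotine dependence is modelled for each SNP "using genotype after adjusting for smoking dose (pack-years), age and recruitment setting using logistic regression (LR"). A further regression will "correlate the proportion of African ancestry with FTND score (low vs. high) after adjusting for smoking dose, age and recruitment setting". No adjustment covariates are stated for the penalised logistic model.
- **Aim 3, Section 13.0.** This is the only place where site is a covariate, in a list of terms the team will consider: "demographics, numeracy, FTND, study site, gender, age". Section 4.1 has Aim 3 randomisation run independently at each site.
- **Recruitment, Section 4.0.** The 180 clinic and 180 community participants are each drawn from both cities. The two settings are matched on age and gender, not on city.
- **Specimens, Section 12.0.** "Only coded bio-specimens will be sent to FCCC where all laboratory procedures will take place".

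No section gives Aims 1 or 2 a city or site term, stratification by site, or a sensitivity analysis by site.

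**The concern.** Aims 1 and 2 are observational, so only the covariates in the model protect a marker comparison from a common cause. City is a candidate. The two samples may differ in ancestry mix, and the markers are selected because their frequency varies with ancestry. NNAL may differ by city through products smoked, local exposure or specimen handling. FTND may differ through the make-up of the local samples. Pack-years captures only part of any exposure difference, and recruitment setting captures none of a city difference that is present in both settings.

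If both conditions hold, a marker with no effect is associated with the outcome. A city difference in ancestry would shift many markers at once, so the error would not be confined to one test. At stake is whether the list of declared markers can be read at the stated error rate. The plan lists site where randomisation already handles it and omits it where nothing else does.

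**Working it through.** **Inputs from Section 13.0.** Aim 1: 360 samples split 1:3 (90 and 270), log2 total NNAL with SD 1, effect 0.45, two-sided 0.005. Aim 2: 180 per dependence group.

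**Assumptions.** 180 per city, taken from the Section 4.1 table (180 at FCCC, 180 at collaborating institutions). Overall carrier share 25%, from the 1:3 split. The city gaps below are assumed, because the documents give none.

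**1. The plan's own figure.** SE = sqrt(1/90 + 1/270) = 0.1217. Power = Φ(0.45/0.1217 − 2.807) = Φ(0.890) = 81.3%. The stated 80% reproduces.

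**2. Bias for a null marker when city is left out.** Bias = (city shift in NNAL) × [P(city 1 | carrier) − P(city 1 | non-carrier)].
- Carrier gap 0.10 (30% vs 20%): 0.30/0.50 − 0.70/1.50 = 0.600 − 0.467 = 0.133.
- Carrier gap 0.20 (35% vs 15%): 0.35/0.50 − 0.65/1.50 = 0.700 − 0.433 = 0.267.

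The rejection rate is P(|Z + bias/SE| > 2.807). The SE is slightly above 0.1217 because city variation stays in the residual. For gap 0.20 and shift 0.5 SD, the city variance is 0.25 × 0.70 × 0.30 = 0.0525 in carriers and 0.25 × 0.433 × 0.567 = 0.0614 in non-carriers. SE is then sqrt(1.0525/90 + 1.0614/270) = 0.1250, and the mean z is 0.133/0.1250 = 1.07.

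| Carrier gap | NNAL shift (SD) | Bias (log2) | Share of 0.45 | Rate at nominal 0.005 |
|---|---|---|---|---|
| 0 | any | 0 | 0% | 0.005 |
| any | 0 | 0 | 0% | 0.005 |
| 0.10 | 0.25 | 0.033 | 7% | 0.007 |
| 0.10 | 0.5 | 0.067 | 15% | 0.012 |
| 0.20 | 0.5 | 0.133 | 30% | 0.041 |

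Simulation of the last three rows (8,000 runs each, recruitment setting in both models) gave 0.006, 0.011 and 0.040 without a city term, and 0.004 to 0.005 with one.

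**3. The planned decision rule.** The 0.005 level comes from the power text. Aim 1 is decided by Benjamini-Hochberg at 10%. With 200 null markers that all share the gap, simulation gave at least one false discovery in roughly 14% to 17% of runs (gap 0.10, shift 0.25 SD) and 79% (gap 0.20, shift 0.5 SD). With a city term it was about 10%. When every marker is null, this proportion is the FDR.

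**4. Aim 2.** Take a carrier gap of 0.20 and high dependence in 60% vs 40% by city. Carrier share is 0.60 × 0.35 + 0.40 × 0.15 = 0.27 in the high group and 0.40 × 0.35 + 0.60 × 0.15 = 0.23 in the low group. The spurious odds ratio is (0.27 × 0.77)/(0.23 × 0.73) = 1.24. Upper-tail rejection at nominal 0.005 is about 0.027. With a carrier gap of 0.10, the odds ratio is 1.11 and the rate about 0.009.

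**5. Outcome difference only.** With no carrier gap, a 0.5 SD city shift raises the residual SD to sqrt(1 + 0.5² × 0.25) = 1.031, about 3%. That is noise, not bias.

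**6. Cost of the city term.** R² between marker and city = (gap/2)²/(0.25 × 0.75), which is 0, 0.0133 and 0.0533 for gaps 0, 0.10 and 0.20. Power for 0.45 = Φ(3.697 × sqrt(1 − R²) − 2.807) = 81.3%, 80.7% and 78.5%.

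**The case against.** The strongest reply is that the harm is hypothetical. It needs a city gap in marker frequency and a city gap in the outcome, both remaining after pack-years, age and setting, and the documents supply neither. At a carrier gap of 0.10 with a 0.25 SD shift, the rate is 0.007 against 0.005. A gap of 0.20 means 15% carriers in one city and 35% in the other, which is large for two samples of African American smokers. The pack-years adjustment would also remove part of any exposure difference. All of this stands, and it limits the claim to a conditional one.

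Four stronger readings are tempting, and the documents do not support them.

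- **The FDR is broken.** A reader might take it that the 10% rate will not be held. That follows only under assumed gaps. Larger ones give alarming figures (gap 0.20 with a 1.0 SD shift gives a rate of 0.20), but nothing in the documents points to gaps of that size.
- **Specimen transit biases the markers.** All laboratory work is at FCCC, and the only stated transport condition concerns another specimen: "All mouthwash samples will be transported at 4 degrees Celsius (on ice packs) to the laboratory where they will be processed". Transit could matter only for urinary NNAL in Aim 1, and on its own it adds noise. It cannot affect FTND. No passage shows that NNAL changes in transit or that the mouthwash condition suits urine, so no urine-handling change follows from this point.
- **Recruiting centre would be a better term than city.** Section 4.0 names three centres, while Section 4.1 speaks of two study sites. Hunter recruits from the community. If Mount Sinai recruits mainly through its health system, centre within NYC would largely duplicate setting.
- **A city term settles ancestry confounding.** It does not. The single-marker models still omit proportion of African ancestry, so admixture within each city remains unadjusted.

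**Conclusion.** The omission is certain; its consequence is conditional. Every stated Aim 1 and Aim 2 association model leaves out city, no listed covariate replaces it, and nothing elsewhere in the plan compensates. If marker frequency or ancestry and the outcome both differ by city after the planned adjustments, null markers will be associated with NNAL or FTND, and the 10% FDR could be exceeded. If only one differs, the marker estimates are not biased.

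The true size is unknown and may be negligible. The illustrative false-positive range of 0.007 to 0.041 at nominal 0.005 rests on 180 per city, a 25% carrier share and the assumed gaps. The FDR illustration further assumes that all 200 markers are null and share the same gap. The change is worth making because it is nearly free, and because a city term chosen after seeing the results would carry less weight than one fixed in advance.

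**What to change.** In Section 13.0, add city (Philadelphia vs NYC) as a two-level fixed factor, next to recruitment setting, in:

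- the Aim 1 per-marker, haplotype-block and African-ancestry models;
- the Aim 2 per-SNP logistic model and African-ancestry regression.

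State also that the city term does not address admixture within a city, so that single-marker results are not read as free of ancestry confounding.

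The cost is one degree of freedom and, for the 0.45 effect, 0 to about 3 points of power over carrier gaps of 0 to 0.20. Where NNAL differs by city and marker frequency does not, the term gains a little precision. No new data are needed, since site must already be known for randomisation by site and is a listed Aim 3 covariate. Only the analysis text changes.
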